### **1.3. Description of population**

PIVOTALboost will recruit patients with high risk or intermediate risk (with adverse features) localised prostate cancer who opt to have radiotherapy as radical treatment.

### **1.4. Study rationale**

Following the CHHiP trial, hypofractionated image-guided radiotherapy is anticipated to become the new standard of care for patients with localised prostate cancer undergoing RT. The PIVOTALboost trial will evaluate the need for pelvic node radiotherapy, and depending on staging MRI imaging, of whole gland or focal dose escalation.

## **2. TRIAL OBJECTIVES**

### **2.1. Primary objective**

The primary objective of PIVOTALboost is to assess whether pelvic lymph node radiotherapy with or without dose escalation to the prostate with HDR, HDR incorporating a focal boost or focal boost IMRT when delivered at multiple centres can lead to improved failure free survival with similar levels of bladder (genitourinary) and bowel (gastrointestinal) side effects experienced by patients.

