### **13.6. Analysis plan**

The principal analysis will occur after a median follow-up of five years or the target numbers of events have been reached, whichever occurs first. A total of 820 events (217 events x 2 (A, B) + 193 events x 2 (C, D)) to detect a difference of 7% with 85% (A vs B) or 80% (A vs C, D) power is required. Should the analysis not be event driven, the timing will be subject to approval from the IDMC.

The primary comparisons will compare each of the experimental arms to the standard (i.e. A vs B, A vs C and A vs D) and will include all randomised patients (intention-to-treat analysis). Only contemporaneously randomised controls will be used for the A vs C and A vs D comparisons. As secondary analyses, comparisons between experimental arms will also be reported, as well as the overall impact of prostate IMRT vs prostate and pelvis IMRT (A+C vs B+D) and no prostate boost vs prostate boost (A+B vs C+D). Exploratory analysis of the heterogeneity of treatment effect across whole gland or focal boosts, and type of focal boost (IMRT or HDR) will be performed.

All treatment effects will be presented with 2-sided 95% confidence intervals. Adjustment will be made for multiple testing as appropriate. Time to event endpoints will be summarised presenting estimated Kaplan-Meier curves (by treatment); the time point of primary interest is 5 years from randomisation, which will be presented with 95% CI for each treatment arm. Treatment effects will be estimated and tested for significance by the Cox proportional hazards model, adjusting by stratification factors.

Adjusted models will include the duration of ADT prior to starting radiotherapy (as a result of COVID19 related delays to radiotherapy starting). Further models adjusting by other important known prognostic factors will also be fitted. Methods to account for non-proportionality will be used if appropriate. Acute and late side effects will be summarised as frequencies and percentages at each time point. Acute toxicity will also be summarised as worst toxicity reported during radiotherapy. The proportion experiencing grade $\geq$ 2 side effects will be presented; comparisons between treatment groups will be tested using chi-squared or Fishers exact tests. Logistic regression models will be used to estimate treatment differences (odds ratios). Analysis of QL and health economic endpoints are further detailed in Section 20.

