### **13.7. Interim analyses and stopping rules**

Adherence to dose volume constraints will be checked after 30 patients are recruited to each experimental arm to ensure treatment can be delivered within safe constraints. Adherence to treatment will be monitored closely during recruitment: in particular any delays or interruptions of more than 5 days of treatment will be escalated to the Trial Management Group.

The IDMC will review emerging safety and efficacy data at regular intervals (at least annually).

Once 119 patients have been recruited to each of the experimental arms (B, C, and D) and completed their week 18 toxicity assessment an interim safety analysis will be conducted to rule out 30% (or more) patients with RTOG grade 2 or worse bladder or bowel complications. The figure has been estimated assuming an expected rate of 20% in the control group (inferred from data for all patients in the PIVOTAL study) and powered (80% power, 0.05 one-sided  $\alpha$ ) with a one-stage A'Hern design. If 27 or more patients out of 119 in one group developed bladder or bowel complications of grade 2 or more at 18 weeks, consideration will be given to modifying the trial design by dropping the treatment arm. As the recruitment pattern for arm B is different to arms C and D this analysis will be carried out as the data for each of the experimental arms matures.

No formal early stopping rule for futility or efficacy for the primary endpoint (FFS) has been planned.

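### The primary objective includes similar bladder and bowel toxicity, but section 13.6 fixes tests of a difference with no limit on the excess, and its worst-grade summary does not cover a common period for HDR patients

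*Protocol*

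**What the plan says.** The Trial Summary and section 2.1 pair the efficacy claim with a toxicity claim: "can lead to improved failure free survival with similar levels of bladder (genitourinary) and bowel (gastrointestinal) side effects experienced by patients". The primary endpoint, the sample size and the alpha of 0.017 per comparison concern failure-free survival alone (sections 4.1 and 13.1). Acute toxicity at 18 weeks and late toxicity are secondary endpoints (section 4.2).

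Section 13.6 sets out the toxicity analysis:
- description: "Acute and late side effects will be summarised as frequencies and percentages at each time point";
- an additional summary: "Acute toxicity will also be summarised as worst toxicity reported during radiotherapy";
- for the proportion with grade 2 or worse: "comparisons between treatment groups will be tested using chi-squared or Fishers exact tests";
- estimation: "Logistic regression models will be used to estimate treatment differences (odds ratios");
- for every effect: "All treatment effects will be presented with 2-sided 95% confidence intervals".

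Section 13.7 adds a safety check in each experimental arm once 119 patients have reached week 18: "an interim safety analysis will be conducted to rule out 30% (or more) patients with RTOG grade 2 or worse" bladder or bowel complications, with 20% as the expected rate.

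**The concern.** Similarity is a statement that any excess is smaller than some stated amount. A test of no difference addresses another question, and failing to reject it may only mean that the comparison is imprecise. Section 13.6 supplies the test and the interval but gives nothing to read the interval against. Section 1.2.2 accepts that boost schedules may be more toxic than prostate-alone treatment, so the question is a live one. If an experimental arm improves failure-free survival, the toxicity half of the objective bears directly on whether practice should change.

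The worst-grade summary raises a smaller question. If its period depends on how treatment is delivered, the arms are not being compared over the same time.

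**Working it through.** **The plan's own toxicity figure.** Section 13.7 gives 119 patients per experimental arm (20% against 30%, one-sided 0.05, 80% power, one-stage A'Hern design). By exact binomial, accepting up to 27 events in 119 gives an error rate of 0.048 at a true 30% and power of 0.804 at a true 20%, so 119 reproduces. The printed trigger of 27 or more events accepts only up to 26, which gives 0.030 and 0.737. That is a separate mismatch within section 13.7, and the passage must be reconciled. For the present point, what matters is that this check is single-arm and makes no comparison with A.

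**Inputs for the between-arm comparison.** Appendix A4 gives A (within the boost randomisation) 144 + 246 = 390, and C or D 212 + 246 = 458 each; A and B have 517 each. The grade 2+ rate in A is the 20% of section 13.7. All patients are taken as assessed.

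**Step 1: what the planned test misses.** For A against C or D and a true rise from 20% to 25%:
- pooled rate = (390 × 0.20 + 458 × 0.25) / 848 = 0.227
- SE under no difference = √[0.227 × 0.773 × (1/390 + 1/458)] = 0.0289
- SE under the true rates = √[0.16/390 + 0.1875/458] = 0.0286
- power = Φ[(0.05 − 1.96 × 0.0289) / 0.0286] = Φ(−0.23) = 0.41, so 59% of trials are non-significant.

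The same formula gives the chance of a non-significant result:

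| True rate in experimental arm | A vs B, 0.05 | A vs C or D, 0.05 | A vs B, 0.017 | A vs C or D, 0.017 |
|---|---|---|---|---|
| 22.5% | 84% | 86% | 92% | 93% |
| 25% | 51% | 59% | 68% | 75% |

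**Step 2: what the interval can support.** At 20% in both arms, the SE of the difference for A vs C or D is √[0.16 × (1/390 + 1/458)] = 0.0276, a 95% half-width of 1.96 × 0.0276 = 5.4 points. For A vs B the SE is 0.0249 and the half-width 4.9 points. If the true rates are equal, the power to place the upper 95% limit below a value m is Φ(m/SE − 1.96):

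| Limit m (assumed; the protocol states none) | A vs B | A vs C or D |
|---|---|---|
| 10 points | 98% | 95% |
| 7.5 points | 85% | 78% |
| 5 points | 52% | 44% |

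With a 98.3% interval, the A vs C or D figures are 89%, 63% and 28%.

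**Step 3: the worst-grade period.** No rates are available here, so the sections are set side by side.
- Sections 10.1 and 10.5: HDR patients in arm C have 15 external beam fractions. A, B, focal-IMRT C2 and D2, and HDR patients in D have 20. At five fractions a week (section 10.6) that is three treatment weeks against four.
- Section 10.5: the implant is normally 14 to 21 days before external beam treatment. By local standard and with QA approval it may come two to three weeks after. The first acute assessment is in week 1 of external beam treatment.
- Sections 8.3 and 8.4: forms are weekly during treatment, then at weeks 6, 8, 12 and 18 from the first external beam fraction.

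The implant therefore lies outside the external beam weeks in either sequence. When it comes second, its acute effects reach only the later forms, outside a summary read as the external beam weeks.

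**The case against.** The strongest reply is that the protocol nowhere says similarity will be concluded from p > 0.05. That is true. A reader might infer such a rule because no other is given, but section 13.6 also requires odds ratios and 95% intervals, and section 20.2 compares patient-reported symptoms between arms. A careful reader could judge similarity from the interval. What remains is that no limit is named to judge it against.

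A second reply is that details belong in the statistical analysis plan, to which section 13.6 defers, and that toxicity is a secondary endpoint. A missing margin alone would be a fair matter for that plan. But the protocol itself states the objective and fixes tests that do not match it, so those two passages need aligning in any case. The section 13.7 check does not fill the gap: it is single-arm and confined to week 18.

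On the worst-grade summary, the other side is largely right about weight. It is an extra summary. The named week 18 endpoint is timed alike in every arm, and weeks 6, 8 and 12 are reported for all. The follow-up summary and the schedule table list treatment weeks 1 to 4 without distinguishing arms, so three forms for 15-fraction patients is a reading of the fraction count. A reader might also infer that the period flatters HDR. The documents do not support that: HDR normally comes first, and section 12.5 asks for the highest grade since the previous visit, so the week 1 form may reach back over the post-implant interval.

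Finally, 20% against 30% in section 13.7 is an absolute safety limit, not an agreed excess over A. It cannot be carried to late toxicity, where section 1.1.8 cites cumulative grade 2+ rates of 7% for bladder and 0% for bowel in pilot studies.

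**Conclusion.** The point holds as a mismatch between the objective and the fixed analysis. If the difference test were the basis for calling toxicity similar, a 5-point rise would pass as non-significant in 59% of A vs C or D comparisons and 51% of A vs B comparisons at 0.05. These figures assume 20% grade 2+ in A for bladder or bowel combined, the arm sizes of Appendix A4, and complete assessment. The planned arms can support a similarity claim at a 10-point limit, only moderately at 7.5, and poorly at 5, so the choice of limit decides what can be claimed.

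The worst-grade point is secondary and confined to HDR patients: the shorter course affects those in arm C, and the implant timing affects HDR patients generally. A, B and focal-IMRT C2 and D2 are unaffected. Neither the size nor the direction of any bias can be established from the protocol. Overall this is a cheap improvement, not a flaw that undermines the trial.

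**What to change.** In section 13.6, report the risk difference (experimental minus A) in RTOG grade 2+ bladder and bowel toxicity with its confidence interval, at week 18 and for late toxicity. State that similarity is judged on the upper confidence limit and not on a non-significant test.

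The sponsor should set and justify the limit before comparative data are seen. The section 13.7 contrast is a possible starting point for week 18 only; late toxicity needs its own limit. If the sponsor does not wish to fix a limit, reword the objective in section 2.1 and the Trial Summary so that toxicity is described and not claimed to be similar.

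Define worst acute grade as the maximum over all acute assessments from first treatment (HDR or external beam) to week 18, in every arm.

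The cost is wording: the data are already collected, and no extra patients are needed at a 10-point limit. The downside is that a limit is fixed in advance and the similarity claim becomes harder to make.

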### **2.2. Secondary objectives**

Secondary objectives of PIVOTALboost are to assess:

- Acute bladder and bowel toxicity of hypofractionated prostate radiotherapy at 18 weeks
- Late toxicity
- Quality of life
- Time to loco-regional recurrence, time to biochemical or clinical failure, metastatic relapse free survival, overall survival and prostate cancer specific survival; time to recommencement of androgen deprivation therapy
- Health economic endpoints.

### **2.3. Exploratory and translational objectives**

PIVOTALboost will assess the usefulness of functional MRI imaging to select patients for different randomisation streams. Boost volumes (staging MRI scan), planning boost volumes and dose volume histograms will be analysed and compared with toxicity outcomes. In addition, and subject to successful funding applications the following sub-studies are proposed:

- Imaging sub-studies to explore the role of PSMA PET imaging for staging and boost volume outlining.
- Translational projects to include a genetic signature analysis to evaluate risk group stratification and collaboration with RAPPER project.

### 3. TRIAL DESIGN

PIVOTALboost is a multicentre randomised controlled phase III trial in patients with localised prostate cancer, with a 4-arm parallel design. Patients will be allocated to one of the following treatment arms:

- A: Prostate alone IMRT
- B: Prostate and pelvic IMRT
- C: Prostate IMRT and prostate boost.
- D: Prostate and pelvic IMRT and prostate boost.

This parallel group design will allow pair-wise comparisons of each of the experimental arms (B, C or D) with the control arm (A). Randomisation into arms C and D will depend on the boost volume identified by MRI (suitable for focal boost or not), availability of focal HDR or IMRT, and patient suitability for focal IMRT or HDR (see section 10 for further details). Treatment allocation will be by minimisation (with a random component) within each randomisation option (see section 10 and 13 for further details).

#### Box 1. Suitable focal boost volume

In summary, a **suitable focal boost** volume is defined as:

On the **pre-biopsy** staging multiparametric MRI (mpMRI) scan, a dominant intra-prostatic lesion (DIL) has:

- A score 4 or 5 lesion (clinical significant cancer is likely or highly likely to be present) according to the (PI-RADS (v.2) guidelines. Both T2 and DWI are important and this depends on tumour location in the gland.
- DIL >5mm axial dimension – minimum (>10mm if patient is NCCN intermediate risk).
- Total DIL volume estimated to be <50% total prostate volume. If there are 2 or 3 DILs, add the individual volumes. Volumes can be estimated with measurement of dimension in 3 directions.

Patients with **post-biopsy MRI** won't be eligible for a focal boost, but can receive a whole gland boost if suitable for HDR.

Patients will be assessed weekly during RT, then at 6, 8, 12, 18 weeks; 6, 12, 18 and 24 months, then annually up to 10 years from the start of RT. RT side effects and patient reported outcomes will be assessed up to 5 years. Longer-term follow-up will include PSA levels (routine testing) and details of disease recurrence and deaths.

For certain time period/s during the COVID19 pandemic recruitment may be suspended, restricted or focussed to certain (otherwise eligible) patient groups (e.g. to those geographically close to treatment centres). Details of these changes to the eligible population will be circulated to all open centres and included in the Trial Master File.

### 4. STUDY ENDPOINTS

#### 4.1. Primary endpoint

Failure-free survival (FFS), defined by the time from randomisation to first biochemical failure, recommencement of androgen deprivation therapy, local recurrence, lymph node/pelvic recurrence, distant metastases or death due to prostate cancer.

Biochemical (PSA) failure is defined following the RTOG-ASTRO Phoenix Consensus definition: an increase in serum PSA  $\geq 2$ ng/ml greater than the post-treatment nadir.

In addition, it is recognised that after high dose radiotherapy a benign PSA bounce is seen in up to 20% of patients, usually within the first 2 years. In some cases the magnitude of the bounce is high enough for the patient to be incorrectly classified as a PSA failure. To prevent this, PSA failure before 24 months will require

3 consecutive rises in PSA (not less than 6 weeks apart) resulting in a clinical diagnosis of failure, or commencement of further treatment (e.g. ADT). After 24 months, the definition of PSA failure for patients receiving radiotherapy will revert to the Phoenix definition described above (i.e. nadir+2 ng/ml).

#### **4.2. Secondary endpoints**

- Time (from randomisation) to loco-regional recurrence (local or lymph node/pelvic recurrence);
- Time (from randomisation) to biochemical or clinical failure, defined by the time from randomisation to first biochemical failure, recommencement of androgen deprivation therapy, local recurrence, lymph node/pelvic recurrence or distant metastases
- Metastatic relapse free survival (time from randomisation to distant metastases or prostate cancer death);
- Overall survival and prostate cancer specific survival;
- Time to recommencement of androgen deprivation therapy;
- Adherence to dose constraints
- Acute bladder and bowel toxicity at 18 weeks;
- Late toxicity;
- Quality of life;
- Health economic endpoints.

Secondary outcome measures have been selected to comprehensively assess the treatment techniques whilst minimising as far as possible the burden of data collection for participating centres. Though COMET guidelines for localised prostate cancer are not yet available [62], we have taken into account recommendations from the International Consortium for Health Outcomes Measurement (ICHOM) [63].

#### **4.3. Exploratory endpoints**

- Number of patients with no boost volume, boost volume and boost volume >50% identified on the staging MRI;
- Type of MRI sequence (T2W, DWI, DCE or other) and timing (pre-biopsy or post biopsy)

Subject to separate funding application are sub-study endpoints relating to PSMA PET CT staging scans and translational studies.

### **5. PATIENT SELECTION & ELIGIBILITY**

#### **5.1. Number of participants**

Original calculations required 1952 patients: 517 allocated to Arm A, 517 to Arm B, 459 to Arm C and 459 to Arm D with relative numbers between treatment groups 9:9:8:8. The allocation ratio will be monitored and adjusted during the trial to account for number of sites open, and what type of boost is available at each site.

Following closure of Arm B changes to the sample size requirements were made. Recruitment will now be complete when 847 patients have been randomised to Arms A and C and 847 patients have been randomised to Arms A and D. Overall, the total recruitment across all four arms will be 2195 (see section 13 and appendix 4, for details).

## 5.2. Source of participants

Participants will be recruited from participating sites in the UK. Patients will be approached about participation in PIVOTALboost if they are considered (e.g. at multi-disciplinary team meetings) to be fit for radical radiotherapy and fulfil the eligibility criteria. International recruitment from quality assured sites outside the UK may be considered by the Trial Management Group subject to Sponsor and ethics approval and adequate funding.

ICR-CTSU encourages investigators to consider equality, diversity and inclusion when recruiting participants into its trials.

## 5.3. Inclusion criteria

1. Histologically confirmed, previously untreated, non-metastatic adenocarcinoma of the prostate using the Gleason scoring or grade group system (histological confirmation can be based on tissue taken at any time, but a re-biopsy should be considered if the biopsy is more than 12 months old).
2. PSA <50ng/ml prior to starting ADT.
- 3.1. NCCN localised high risk or locally advanced disease
  - T3a, T3b or T4 N0M0 (clinical and/or MRI) and/or
  - Grade group 4 or 5 (Gleason 8-10) and/or
  - PSA >20;or
- 3.2. NCCN intermediate risk disease
  - T2b-c N0M0, and/or Grade group 2 or 3 (Gleason 7) and /or PSA 10-20 ng/mland
  - DIL lesion >10mm on staging MRIand
  - One additional adverse feature, for example: Maximum tumour length (MTL) >6mm and/or ≥50% biopsy cores positive and/or >50% involvement measured in mm cancer length /total biopsy length.
4. Age ≥18 years.
5. Signed, written informed consent.
6. WHO performance status 0-2 (Appendix 1).

## 5.4. Exclusion criteria

1. Prior radiotherapy to the prostate or pelvis.
2. Prior radical prostatectomy.
  - Prior ADT for > 6 months at randomisation. Radiotherapy should start within 6 months of starting ADT. *For patients receiving extended ADT to permit safe delay of radiotherapy as a result of the COVID19 pandemic, the duration of ADT must be less than 12 months prior to commencing radiotherapy.*
3. Adjuvant docetaxel chemotherapy.
4. Radiologically suspicious or pathologically confirmed lymph node involvement, as confirmed by radiological assessment (see section 8.1 screening assessments).
5. Evidence of metastatic disease, as confirmed by radiological assessment (see section 8.1 screening assessments).
6. Life expectancy <5 years.

7. Bilateral hip prostheses or any other implants/hardware that would introduce substantial CT artefacts and would make pelvic node planning more difficult.
8. For patients having fiducials inserted: Anticoagulation therapy/ bleeding tendency making fiducial placement unsafe in the opinion of the clinician.
9. For patients being considered for randomisation options C2 and D2 only and are undergoing a planning MRI scan: Contraindication to undergo a MRI scan.
10. For undergoing HDR brachytherapy: long-term anticoagulation therapy which cannot be temporarily stopped, prostate surgery (TURP) with a significant tissue cavity, a history of recent deep vein thrombosis or pulmonary embolus, significant cardiovascular comorbidity, unfit for prolonged general anaesthetic.
11. Medical conditions likely to make radiotherapy inadvisable e.g. inflammatory bowel disease, significant urinary symptoms.
12. Previous malignancy within the last 2 years (except basal cell carcinoma or squamous cell carcinoma of the skin), or if previous malignancy is expected to significantly compromise 5 year survival.
13. Any other contraindication to external beam radiotherapy to the pelvis.

